1.1 Aortic and peripheral arterial disease

Aortic and peripheral arterial disease are important causes of morbidity and mortality. The prevalence of aortic and peripheral arterial disease (PAD) increases progressively with age, beginning after age 40. Total disease prevalence of PAD is in the range of 3% to 10%, increasing to 15% to 20% in persons over 70 years ^{2,3}. CT angiography (CTA) of the aorta and the lower limb is one of the most important tools for diagnostic, evaluation of the severity of the disease, decision making, treatment planning and follow-up; but usually requires the use of iodine contrast medium.

1.2 Renal impairment

Due to the high prevalence of renal impairment (eGFR < 90 ml/min/1.73m) in the elderly hospitalized population (more than 90% among inpatients aged over 60 years) contrast-medium-induced nephropathy is a major concern in this population.¹ This is found to be correlated with the ratio between dose in gram iodine and eGFR ⁴⁻⁸. Current practice at our hospital is to calculate the maximum amount of iodine contrast medium considered as safe using OmniVis calculator. There is however uncertainty whether this calculator is sufficiently validated for the patient population with stage 3-5 of chronic kidney disease.

1.3 Contrast medium and diagnostic quality

An iodine load of less than 20 g is considered insufficient for a standard diagnostic CT imaging of the abdominal aorta and arteries in the lower limb. The risk of contrast-medium-induced nephropathy has limited options for diagnostic imaging in patients with severely reduced kidney function. Some of these patients have been offered CO₂ angiography which is inferior in diagnostic quality. Others have not received imaging, thereby limiting the therapeutic options.

1.4 Spectral CT

The recently introduced spectral CT technique utilizes x-rays covering a spectrum of energy-levels as opposed to conventional CT in which x-rays are set to one specific energy level. Spectral Detector CT (SDCT) utilises a single X-ray tube but has two layers of detectors to simultaneously collect low and high energy data in all patients.

This technology offers many possibilities, such as “boosting” the x-ray contrast effect of iodine. This improves the vascular enhancement of the contrast medium using low-energy, virtual monoenergetic imaging (VNI).

Akershus University Hospital has recently acquired the first spectral CT scanner in Norway, the Philips iQon.

1.5 This study

We plan to perform a randomized controlled trial for CT examinations of the abdominal aorta and lower extremities. In this RCT, a new ultra-low iodine contrast medium examination procedure tailored for spectral CT on the Philips iQon is compared to the standard examinations.

2 Objectives:

The objectives of this study are:

Evaluation of ultra-low iodine load CTA protocols of the aorta and lower extremities.

To investigate whether dual-layer in combination with virtual monoenergetic imaging (VNI) allows for reduction of contrast medium (CM) in CTA of the aorta and lower limbs with sustained objective and subjective examination quality parameters.

3 Materials and Methods:

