3.2 Population, Sample size and Recruitment (Inclusion & exclusion)

In-patients and outpatients at AHUS.

Sample size: alfa (level of significance): 0.05, beta (power) 80%. Assuming a mean difference of 0.5 points (on the subjective 5-point scale) with a standard deviation between 1 and 1.5 results in a sample size of 100 in each group.

With SD = 0.8 sample size is 50 in each group.

With SD = 1 sample size is 63 in each group.

Med SD 1.5 sample size is 141 in each group.

Estimated inclusion time: 2 years.

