From each imaging examination from the iQon a total of three datasets of vni at 40, 50 keV levels, and conventional, will be reconstructed with spectral 3 level. Conventional images from the control group are compared to vni at 40 and 50 keV in the study group.

For study and control examinations arterial attenuation, image noise, Signal to Noise Ratio (SNR) and Contrast to Noise Ratio (CNR) is recorded.

Arterial attenuation is measured by an experienced radiology technician (where appropriate) in the:

- Abdominal aorta (at the midpoint between the renal arteries and the aortic bifurcation)
- Iliaca communis (at the midpoint between the aortic bifurcation and iliac bifurcation)
- Femoralis superficialis (ca 10 cm inferior to the branching of the deep femoral artery)
- Poplitea (p3 – inferior part of a. Poplitea).

The measurements are performed by placing a region of interest (ROI) within the artery at predefined levels.

Image noise is measured by placing a ROI in air and measuring the standard deviation of the attenuation.

Signal to Noise Ratio (SNR) is measured by dividing the mean arterial attenuation (at defined levels) by mean image noise.

Contrast to Noise Ratio (CNR) is measured by dividing the difference between arterial and muscular attenuation by the image noise: (arterial attenuation - muscular attenuation) / Image noise

Vascular pathology is classified according to the TASC II grading system by an interventional radiologist.

Pas id: nummer – (0=standard, 1=studie, a = keV40, b=keV50)

3.5.3 Subjective /semiquantitative assessment of examination quality:

Subjective examination quality will be rated on a 4-point scale separately by 2 interventional radiologists who are blinded to each other's rating. Discrepancies will be resolved by a third rater.

The subjective rating is performed at the same anatomical levels as the objective measurements. Additionally subjective examination quality is rated in the calf as the best of the three arteries: a. tibialis post., a. tibialis ant. eller a. fibularis.

The rating is performed separately on the left and right side and on conventional, MonoE 40 keV and MonoE 50 keV.

Images that cannot be assessed due to metal artifacts such as hip replacements are labelled "missing" - 9.

Rating	Definition
1	Excellent: The demarcation of the vessel lumen is excellent, more than sufficient for confident diagnosis or exclusion of stenosis or occlusion.

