2	Good: The demarcation of the vessel lumen is sufficient for confident diagnosis or exclusion of stenosis or occlusion.
3	Adequate: The demarcation of the vessel lumen is adequate for diagnosis or exclusion of stenosis or occlusion but with limited confidence.
4	Non-diagnostic: There is insufficient demarcation of the vessel lumen for diagnosis or exclusion of stenosis or occlusion.
8	Thrombosis or occlusion at this anatomic level. Enhancement cannot be assessed
9	Missing

3.6 End points:

3.6.1 Primary endpoint:

Mean attenuation in the aorta, common and external iliac artery, femoral artery.

3.6.2 Secondary endpoints:

Rate of diagnostic quality angiography (defined as arterial enhancement > 200 HU)

Subjective examination quality

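### The aim is sustained quality at reduced iodine, but the plan sets no margin or rule for concluding it, and a non-significant difference would not show it

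*Combined protocol and SAP*

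**What the plan says.** Section 2 (Objectives) asks whether the technique "allows for reduction of contrast medium (CM) in CTA of the aorta and lower limbs with sustained objective and subjective examination quality parameters". Section 4.1 adds that study examinations are expected to match standard ones or do better.

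Section 3.2 sizes the trial on the rating: "Assuming a mean difference of 0.5 points (on the subjective 5-point scale", then "with a standard deviation between 1 and 1.5 results in a sample size of 100 in each group". It sets significance at 0.05 and power at 80%, without saying whether the test is one- or two-sided, and also lists sizes for SD 0.8, 1 and 1.5.

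The primary endpoint (3.6.1) is different: "Mean attenuation in the aorta, common and external iliac artery, femoral artery". Subjective quality is secondary (3.6.2), as is "Rate of diagnostic quality angiography (defined as arterial enhancement > 200 HU". For the objective measures, section 3.5.2 says: "Conventional images from the control group are compared to vni at 40 and 50 keV in the study group". Section 3.5.3 says: "Subjective examination quality will be rated on a 4-point scale", where 1 is excellent and 4 is non-diagnostic.

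Section 3.7 is three lines: descriptive statistics, a comparison of study and control, and inter-observer agreement. It names no hypothesis, margin, interval or test.

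**The concern.** The study arm's benefit is its lower iodine load, which the design guarantees. What the trial has to establish is that quality is not materially lost. That needs a stated acceptable loss and a rule for ruling it out. The plan has neither.

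Three items come close, and none of them is such a rule:

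- The 0.5 points in 3.2 is a difference assumed for sizing. It is never called tolerable, and it refers to a 5-point scale that 3.5.3 does not use.
- The 200 HU cut-off classifies examinations. It does not say how much lower the study arm's rate or mean may be.
- The rating categories describe one vessel level, not a difference between arms.

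Without a rule, the natural default is to test for a difference and read non-significance as no loss. That inference fails when the confidence interval still contains a loss that matters.

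The gap also works in the other direction. Attenuation is compared across different reconstructions, and section 1.4 says low-energy images boost the iodine signal. A significantly lower study mean would not by itself show a loss that matters, and a non-significant one would not show that quality was sustained. With two keV levels and no lead comparison named, the conclusion could also be settled after the results are seen.

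**Working it through.** **Inputs.** From 3.2: 100 per group, alpha 0.05, power 80%, difference 0.5 points, SD 0.8, 1 and 1.5. Assumed: SD 0.6, as a plausible value for a per-patient summary on the 1–4 scale, and a true worsening of 0.25 points. Normal approximations throughout.

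**The plan's own sizes.** n per group = 2 × (2.802 × SD / 0.5)², with 2.802 = 1.960 + 0.842 (two-sided 5%, 80% power).

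- SD 1.0: 62.8 (plan 63).
- SD 1.5: 141.3 (plan 141).
- SD 1.26: 99.7 (plan 100, for an SD between 1 and 1.5).
- SD 0.8: 40.2, so 41 (plan 50). This does not reproduce and is not relied on here.

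A one-sided 5% test would give 50 and 112 at SD 1 and 1.5, so the plan's figures fit a two-sided 5% test for a difference.

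**What SDs are possible on a 1–4 scale.** With mean m, the SD cannot exceed √((m − 1)(4 − m)). This is 1.5 at m = 2.5, and √(1.25 × 1.75) = 1.48 at m = 2.25 or 2.75. Ratings spread evenly over 1 to 4 have SD √1.25 = 1.12. SD 1.25 to 1.5 is therefore extreme or unattainable on the scale to be analysed, and the main illustration uses 0.6 to 1.0.

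**What non-significance would mean at 100 per group.**

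- SE = SD × √(2/100).
- P(non-significant | true loss d) = Φ(1.96 − d/SE) − Φ(−1.96 − d/SE).
- A result just short of significance has an estimate of 1.96 × SE, so its 95% interval reaches a loss of 2 × 1.96 × SE.

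| SD | SE | Non-significant, d = 0.25 | Non-significant, d = 0.5 | Interval reaches |
|---|---|---|---|---|
| 0.6 | 0.0849 | 16% | under 0.1% | 0.33 |
| 0.8 | 0.1131 | 40% | 0.7% | 0.44 |
| 1.0 | 0.1414 | 58% | 6% | 0.55 |

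The last column equals 0.5 at SD 0.90. Limiting cases only: at SD 1.25 and 1.5 the entries are 71% and 78% (d = 0.25), 19% and 35% (d = 0.5), and 0.69 and 0.83 points.

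**Non-inferiority at the same n.** Power = Φ(margin/SE − 1.96), one-sided 0.025, true difference 0.

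| Rating margin | SD 0.6 | SD 0.8 | SD 1.0 |
|---|---|---|---|
| 0.5 | over 99.9% | 99% | 94% |
| 0.3 | 94% | 76% | 56% |
| 0.25 | 84% | 60% | 42% |

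For a 0.5-point margin the sample-size formula is the one above, so n is unchanged.

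**Primary endpoint.** The plan gives no SD in HU, so power for an HU margin cannot be computed. In SD units, 80% power at 100 per group needs a margin of at least 2.802 × √(2/100) = 0.40 SD.

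**Rate above 200 HU.** The half-width of the 95% interval for the difference is 1.96 × √(2p(1 − p)/100): about 11, 8 and 6 percentage points if both arms are at 80%, 90% and 95% (assumed).

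**Joint requirement.** If two endpoints must both pass and each has 80% power, joint power lies between 0.80 + 0.80 − 1 = 60% and 80%.

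**The case against.** Four points can be made for the plan.

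*It never says that non-significance will count as success.* Correct. A reader might infer that the sponsor intends to read it that way, but no section says so. What stands is narrower: the central conclusion has no rule at all.

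*The sample size is sound.* A reader might infer that a trial sized for a difference must be wrongly sized for non-inferiority. The arithmetic does not support that, since a 0.5-point margin at one-sided 0.025 gives the same n. But the equality helps only if 0.5 points is justified as a tolerable loss, and the plan does not do this.

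*The alarming error rates come from SDs the scale can hardly produce.* This stands. The 19% and 35% chances of missing a 0.5-point loss belong to SD 1.25 and 1.5, which are near or at the ceiling of a 1–4 scale. Below an SD of about 0.90, a non-significant result does exclude a 0.5-point loss. It need not exclude a smaller one, and the attenuation endpoint is untouched by this argument.

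*The first objective is simply evaluation, so estimates with intervals would do.* Intervals would inform the question, but none are planned. Without a stated acceptable loss they would not settle whether quality was sustained. A formal non-inferiority test is not the only possible repair, but some pre-stated criterion is needed.

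**Conclusion.** The concern holds. The plan asks a no-worse-than-standard question, sizes the trial as a test for a difference in a secondary endpoint, and gives no margin or rule for its main conclusion on any endpoint. This should be settled before the arms are compared, because a margin chosen afterwards is not credible.

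The size depends on the rating SD, which the documents do not give for the 4-point scale. Over SD 0.6 to 1.0, a true 0.25-point loss would go undetected in 16% to 58% of trials and a true 0.5-point loss in under 0.1% to 6%. Both 0.25 points and SD 0.6 are assumptions. The verdict does not depend on them: whatever the SD, a non-significant difference is not evidence of sustained quality unless its interval excludes a loss fixed in advance.

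No claim is made that the sample size is wrong or that the sponsor plans to misread a non-significant result.

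**What to change.** Amend section 3.7 before the arms are compared:

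1. State a non-inferiority hypothesis and name one keV reconstruction for the main comparison.
2. Pre-specify and justify a margin for mean attenuation and one for the rating. The 0.5 points in 3.2 is a candidate rating margin once the 5-point and 4-point scales are reconciled. Because mean HU is compared across different reconstructions, either justify the HU margin on that basis or also set a margin for the rate above 200 HU.
3. Conclude that quality is sustained only if the 95% confidence interval for study minus control excludes a loss as large as the margin. For the rating, where higher is worse, the upper limit must lie below the margin. For attenuation and for the rate, the lower limit must lie above minus the margin. Say whether all named endpoints must meet this.
4. State that non-significance will not be read as sustained quality.
5. Restate power at 100 per group for the chosen margins, using an SD for the 4-point per-patient summary that will be analysed.

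The cost is protocol wording and the work of justifying the margins. No new data are needed, and a 0.5-point rating margin leaves n as it is. The downside is that stated power may look worse for a tighter margin (56% for 0.3 points at SD 1.0), for an HU margin under 0.40 SD, or for a joint requirement. That should be reported as it stands rather than met by enrolling more patients.

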3.1 Design

Randomized Controlled Trial.

Patients consenting to participation will be randomized to either examination by standard protocol or examination with ultra-low contrast medium protocol on the iQon scanner. Randomization will be conducted by opening consecutive numbered envelopes which assigns the patient either to "study" or "control".

3.2 Population, Sample size and Recruitment (Inclusion & exclusion)

In-patients and outpatients at AHUS.

Sample size: alfa (level of significance): 0.05, beta (power) 80%. Assuming a mean difference of 0.5 points (on the subjective 5-point scale) with a standard deviation between 1 and 1.5 results in a sample size of 100 in each group.

With SD = 0.8 sample size is 50 in each group.

With SD = 1 sample size is 63 in each group.

Med SD 1.5 sample size is 141 in each group.

Estimated inclusion time: 2 years.

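### 100 per group gives 80% power only up to an SD of about 1.26, not across the stated range of 1 to 1.5, and the sizing uses a 5-point scale while the trial rates on a 4-point scale

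*Combined protocol and SAP*

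**What the plan says.** All sample-size text is in section 3.2 of the combined protocol and SAP. It sets alpha at 0.05 and power at 80%. The target is given as "Assuming a mean difference of 0.5 points (on the subjective 5-point scale"), and this difference "with a standard deviation between 1 and 1.5 results in a sample size of 100 in each group". Three further lines follow: "With SD = 0.8 sample size is 50 in each group", then 63 per group for SD 1, then "Med SD 1.5 sample size is 141 in each group". No single SD is named for the 100.

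Section 3.5.3 describes the rating itself: "Subjective examination quality will be rated on a 4-point scale". Its table defines grades 1 (excellent) to 4 (non-diagnostic). Two further codes are not grades: 8 for thrombosis or occlusion at the level, and 9 for missing. On code 9 the text says "Images that cannot be assessed due to metal artifacts such as hip replacements are labelled" as missing. No 5-point scale is defined anywhere.

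Section 3.6.2 lists subjective quality as a secondary endpoint. Section 3.7 plans a comparison between the groups but names no test.

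**The concern.** The sentence that arrives at 100 reads as if that number holds for any SD from 1 to 1.5. The plan's own line for SD 1.5 asks for 141, so it cannot. The 100 must belong to some SD inside the range, which the plan neither names nor justifies.

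The difference and the SDs are also expressed on a scale that the trial does not use. Neither is restated for the 1-to-4 scale, so a reader cannot tell what power 100 per group gives for the rating that will be analysed. One objective in section 2 is that subjective quality is sustained. If power is lower than stated, a failure to find a difference could be misread as support for that objective.

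**Working it through.** **Inputs.** From section 3.2: difference 0.5, alpha 0.05, power 80%, SDs 0.8, 1 and 1.5, and group sizes 50, 63, 141 and 100. Assumptions: a two-sided test and equal groups (the plan states neither, but they reproduce its lines for SD 1 and 1.5), and a two-sample t-test for the power figures.

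**Step 1. Reproduce the plan's lines.** Normal approximation: n per group = 2 × (1.96 + 0.8416)² × SD² / 0.5² = 62.79 × SD².

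| SD | Plan | Normal approx. (rounded up) | t-test (rounded up) |
|---|---|---|---|
| 0.8 | 50 | 40.19 (41) | 41.17 (42) |
| 1.0 | 63 | 62.79 (63) | 63.77 (64) |
| 1.25 | not given | 98.11 (99) | 99.08 (100) |
| 1.5 | 141 | 141.28 (142) | 142.25 (143) |

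The lines for SD 1 and SD 1.5 reproduce; 141 against 142 is only rounding. The SD 0.8 line does not. A result of 50 needs SD = √(50 / 62.79) = 0.89. At SD 0.8, 50 per group would give 87.2% power.

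**Step 2. Find the SD that belongs to 100.** Normal approximation: SD = √(100 / 62.79) = 1.262. By t-test it is 1.256. The figure of 100 therefore fits an SD of about 1.25.

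**Step 3. Test the range claim.** t-test power with 100 per group for a 0.5-point difference:

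| SD | Power |
|---|---|
| 1.0 | 94.0% |
| 1.25 | 80.4% |
| 1.3 | 77.2% |
| 1.4 | 71.0% |
| 1.5 | 65.0% |

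One-sided testing does not rescue the claim. It would still need 112 per group at SD 1.5, and it gives 50 rather than the plan's 63 at SD 1.

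**Step 4. Move to the 4-point scale.** For ratings between 1 and 4 with mean m, the largest possible variance is (4 − m)(m − 1). It peaks at m = 2.5, where it is 1.5 × 1.5 = 2.25, so SD 1.5. Two arms whose means differ by 0.5 cannot both sit at 2.5. The largest SD they can share is at means 2.25 and 2.75: √(1.75 × 1.25) = √2.1875 = 1.479, with every rating a 1 or a 4.

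For comparison, ratings spread evenly over 1, 2, 3 and 4 have variance (2.25 + 0.25 + 0.25 + 2.25) / 4 = 1.25, so SD 1.118. With a 0.5-point difference, t-test power at that SD is 88.2% with 100 per group.

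**Step 5. Allow for unrated images.** Codes 8 and 9 give no grade. The plan states no rate, so 90 assessable per group is an illustration only. Power is then 91.6% at SD 1.0, 84.7% at SD 1.118 and 76.1% at SD 1.25.

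**The case against.** The best defence is that nothing is hidden. The figures 63 and 141 stand directly below the 100, so a reader can see that 100 is a compromise and that SD 1.5 needs more. That is fair, and it limits the point: 100 is a sound result for an SD near 1.25. But the sentence still credits 100 to the whole range, and the SD behind it is neither named nor justified.

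The second defence is stronger. A reader might infer that the trial has only 65% power for the rating. The documents do not support that. The 65% belongs to SD 1.5 with a 0.5-point difference, a combination that two arms cannot both show on a 1-to-4 scale. An SD above 1.26 there needs ratings concentrated towards both extremes. If 0.5 points is kept, the shorter scale makes 100 look better, not worse. The 65% remains valid only as a check on the range claim as written. If instead the difference and the SDs all shrink by 3/4 (an assumption: 0.375, and 0.75 to 1.125), power stays at 94% to 65%. This is why the sponsor must restate both values.

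A reader might also infer that 100 leaves no margin for codes 8 and 9. That holds only near SD 1.25. At SD 1.0 the plan's own requirement is 63, which leaves 37 per group. The codes apply by level and side, so one coded segment need not remove a patient if ratings are combined.

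Finally, the plan does not name the per-patient rating or the reconstruction contrast that the SD describes. Ratings are plentiful: "The rating is performed separately on the left and right side and on conventional, MonoE 40 keV and MonoE 50 keV". The contrast "Conventional images from the control group are compared to vni at 40 and 50 keV in the study group" is stated under the objective analysis in section 3.5.2. Naming both would help, but this is missing detail and not part of the error.

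**Conclusion.** The point holds in a limited form. As written, three things in section 3.2 are wrong:

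- 100 per group does not give 80% power across SD 1 to 1.5. It does so up to about 1.26, roughly the lower half of the range.
- The SD 0.8 line should read 41 (normal approximation) or 42 (t-test), not 50. The error is conservative and does not affect the 100.
- The scale contradicts section 3.5.3, and the upper end of the SD range cannot be carried to the 4-point scale with a 0.5-point difference.

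The conclusion on power rests on a two-sided test, equal groups and a t-test. The normal approximation gives nearly the same threshold (1.262 against 1.256). It does not follow that the trial is too small: the documents give no SD for the 4-point scale, and 100 per group may be adequate there. The rating is a secondary endpoint, which limits the consequences, but this is the plan's only sample-size justification. It should be corrected.

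**What to change.** 1. Change the scale in section 3.2 to the 4-point scale of section 3.5.3. State on it the target difference and one planning SD, with a reason for each.
2. Replace the claim that SD 1 to 1.5 leads to 100 with the power that 100 assessable patients per group gives at the planning SD and over a plausible range. If 0.5 points is kept, suitable text would be: *With 100 assessable patients per group (two-sided 0.05, two-sample t-test), power for a 0.5-point difference on the 4-point scale is about 94% at SD 1.0, 88% at SD 1.12 and 80% at SD 1.25; 80% is not reached above an SD of about 1.26. Ratings coded 8 or 9 can lower the assessable number; with 90 per group, as an illustration, power is 92%, 85% and 76%.* If the restated difference is not 0.5, recompute these figures.
3. Compute all retained lines by one method. For SD 0.8, 1.0 and 1.25 these are 41, 63 and 99 by normal approximation, or 42, 64 and 100 by t-test. Drop the SD 1.5 line, or mark it as not attainable in both arms on the 4-point scale with a 0.5-point difference.
4. Optional: name the per-patient rating and the reconstruction contrast to which the SD refers.

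The cost is wording only, with no extra patients. The downsides are that the SD range covered at 80% power narrows to about 1.25, and that the sponsor must commit to one difference and one SD. Naming a t-test for the sizing also adds a detail that section 3.7 lacks; for the group-size lines in item 3, the normal-approximation set avoids this.
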